8.14.2. Observation and Recording of AEs

The subject will be required to report any AE that occurs after the main informed consent is signed. SAEs will be reported as outlined in Section 8.16 and recorded in the AE CRF. AEs or SAEs occurring after a subject signs the pre-screening ICF will not be collected.

Study personnel will assess AEs at every visit. The date of onset and resolution (if applicable) of the AE will be documented in the source documents and on the appropriate CRF page. The Investigator will monitor all AEs to the final visit or to a satisfactory resolution if the AE is ongoing.

All AEs will be recorded from the time of signed informed consent until the End of Treatment visit (28 days \pm 7 days after the last dose of JTX-2011, nivolumab, ipilimumab, or pembrolizumab, whichever occurred last), and are to be recorded on the appropriate AE pages in the eCRF and in source documents. AEs for the End of Treatment visit may be collected by a telephone contact if the patient is not able to attend an on-site End of Treatment visit. Where possible, a diagnosis rather than a list of symptoms should be recorded. If a diagnosis has not been made then each symptom should be listed individually.

All study drug related AEs/serious adverse events (SAEs) (see Section 8.16 for definition) will be followed to resolution (the subject's health has returned to his/her baseline status or all variables have returned to normal), or until new therapy initiated. Where appropriate, medical tests and examinations will be performed to document resolution of the event(s).

SAE Reporting Contact Information

Tel: [REDACTED]

Fax: [REDACTED]

Email: [REDACTED]

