¹² For subjects discontinuing treatment for reasons other than disease progression, radiologic assessment will be conducted every 12 weeks (\pm 2 weeks) during the long-term follow-up period until confirmed disease progression or another anti-cancer therapy is initiated.

¹³ Adverse events will be followed up to 28 days post last dose. As the EOT visit can occur anywhere between 21-35 days post last dose any ongoing AEs at the time of the EOT visit can be followed via other contact (e.g., phone or email) up to 28 days post dose. If an SAE occurs 28 days after last dose administered, the event will only be followed if assessed to be at least possibly related to study drug.

¹⁴ Optional Brain MRI to determine eligibility of subjects with documented history of brain metastasis.

¹⁵ Survival can be followed via phone call or email, a clinic visit is not required.

¹⁶ For subjects with prostate cancer only.

¹⁷ If ipilimumab doses are missed on C1D22, C2D1, or C2D22, they can be made up q3w beginning on C3D1. Each subject may receive up to four total doses of ipilimumab.

¹⁸ Ipilimumab PK, ADA, and NAb are only to be collected on C3D1 and beyond if ipilimumab is administered at those visits.

Table 14: Phase 1 q3w in Part G (JTX-2011 + Pembrolizumab)

Timing of Visit	Screening	Cycle 1				Cycle 2	Cycle 3	Cycle 4	Cycle 5	Cycle 6	Cycle 7	Cycle 8 and Beyond	End of Treatment	Long-Term Follow-up
		Day 1	Day 2	Day 4 ¹⁴	Day 8									
Informed Consent	X													
Eligibility Criteria	X	X												
Medical History	X													
Demography	X													
Physical Exam ¹	X	X		X	X ⁴	X ⁴	X ⁴	X ⁴	X ⁴	X ⁴	X ⁴	X		
Weight (kg)	X	X			X ⁴	X ⁴	X ⁴	X ⁴	X ⁴	X ⁴	X ⁴			
ECOG PS	X	X			X ⁴	X ⁴	X ⁴	X ⁴	X ⁴	X ⁴	X ⁴	X		
ECG	X	X ⁴			X ⁴	X ⁴	X ⁴	X ⁴	X ⁴	X ⁴	X ⁴	X		
Vital Signs ²	X	X	X	X	X	X	X	X	X	X	X	X		
Pregnancy test ³	X	X ⁴			X ⁴	X ⁴	X ⁴	X ⁴	X ⁴	X ⁴	X ⁴	X		
Hematology ³	X	X ⁴			X ⁴	X ⁴	X ⁴	X ⁴	X ⁴	X ⁴	X ⁴	X		
Chemistry ³	X	X ⁴			X ⁴	X ⁴	X ⁴	X ⁴	X ⁴	X ⁴	X ⁴	X		
Coagulation Parameters ³	X	X ⁴			X ⁴	X ⁴	X ⁴	X ⁴	X ⁴	X ⁴	X ⁴	X		
Thyroid Function ³	X	X ⁴			X ⁴	X ⁴	X ⁴	X ⁴	X ⁴	X ⁴	X ⁴	X		
Urinalysis ³	X	X ⁴			X ⁴	X ⁴	X ⁴	X ⁴	X ⁴	X ⁴	X ⁴	X		
Cytokines ⁵		X			X	X	X	X	X	X	X			
JTX-2011 ⁶		X			X	X	X	X	X	X	X			
Pembrolizumab ⁷		X			X	X	X	X	X	X	X			
IP ⁵	X	X		X	X	X	X	X	X	X	X			
TE ⁵	X	X		X	X	X	X	X	X	X	X			
PK ⁵		X		X	X	X	X	X	X	X	X			
ADA ⁵		X			X	X	X	X	X	X	X			
Archival Tumor Tissue ⁵	X													
Fresh Biopsy ⁵	X													
NAB ⁵		X			X	X	X	X	X	X	X			

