DNA Blood Sample ⁵		X			X	X	X	X	X	X	X			
RNA Blood Sample ⁵		X			X	X	X	X	X	X	X			
Radiologic Assessment ⁸	X												X ¹⁰	
ConMeds	X	X	X	X	X	X	X	X	X	X	X	X		
AEs	X	X	X	X	X	X	X	X	X	X	X	X		
Optional Brain MRI ¹²	X												X ¹¹	
Survival Status													X ¹³	

Part G Footnotes:

- ¹ A complete physical exam is required at Screening and End of Treatment; otherwise a targeted physical exam is acceptable per institutional guidelines. Height to be calculated at screening visit only.
- ² Vital signs to include temperature, heart rate, respiratory rate, blood pressure, and oxygen saturation. Vital signs should be taken prior to and at the end of JTX-2011 infusion.
- ³ Refer to Section 8.8 for specific lab parameters. Pregnancy test can be serum or urine.
- ⁴ Do not need to be repeated if collected within 72 hours prior to visit.
- ⁵ Refer to the Study Lab Manual for processing/shipping instructions. For specific blood sampling time points, refer to Table 23.
- ⁶ Subjects should be observed for at least 1 hour post-JTX-2011 infusion.
- ⁷ Subjects should be observed for at least 1 hour post-pembrolizumab infusion.
- ⁸ Response will be determined by RECIST (Version 1.1) every 9 weeks (-10 days) prior to Day 1 of every 3rd cycle, (e.g. C4, C7, C10, etc.) until disease progression. The imaging interval may be increased to every 12 weeks with a +/- 3 week window for subjects who remain on study treatment for ≥ 24 months.
The same method of assessment used at baseline should be used throughout the study.
- ⁹ Only required for subjects whose last assessment was > 9 weeks.
- ¹⁰ For subjects discontinuing treatment for reasons other than disease progression, radiologic assessment will be conducted every 12 weeks (± 2 weeks) during the long-term follow-up period until confirmed disease progression or another anti-cancer therapy is initiated.
- ¹¹ Adverse events will be followed up to 28 days post last dose. As the EOT visit can occur anywhere between 21-35 days post last dose, any outstanding AEs at the time of the EOT visit can be followed via other contact (e.g., phone or email) up to 28 days post dose. If an SAE occurs after 28 days after last dose administered, the event will only be followed if assessed to be at least possibly related to study drug.
- ¹² Optional Brain MRI to determine eligibility of subjects with documented history of brain metastasis.
- ¹³ Survival can be followed via phone call or email, a clinic visit is not required.

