- ¹⁴ Day 4 visit required for sentinel subjects only.

Table 15: Phase 2 q3w in Parts C (JTX-2011), D (JTX-2011 + Nivolumab), and H (JTX-2011 + Pembrolizumab)¹⁶

Timing of Visit	Screening		Cycle 1		Cycle 2	Cycle 3	Cycle 4	Cycle 5	Cycle 6	Cycle 7	Cycle 8 and Beyond	End of Treatment	Long-Term Follow-up
	Within 28 days of C1D1	Day 1	Day 2	Day 1 ± 3	Day 1 ± 3	Day 1 ± 3	Day 1 ± 3	Day 1 ± 3	Day 1 ± 3	Day 1 ± 3	Day 1 ± 3	28 ± 7 days post-last dose	Every 12 weeks post-last dose (± 2 weeks)
Informed Consent	X												
Eligibility Criteria	X	X											
Medical History	X												
Demography	X												
Physical Exam ¹	X	X		X ⁴	X ⁴	X ⁴	X ⁴	X ⁴	X ⁴	X ⁴	X ⁴	X	
Weight (kg)	X	X		X ⁴	X ⁴	X ⁴	X ⁴	X ⁴	X ⁴	X ⁴	X ⁴	X	
ECOG PS	X	X		X ⁴	X ⁴	X ⁴	X ⁴	X ⁴	X ⁴	X ⁴	X ⁴	X	
ECG	X	X ⁴		X ⁴	X ⁴	X ⁴	X ⁴	X ⁴	X ⁴	X ⁴	X ⁴	X	
Vital Signs ²	X	X	X	X	X	X	X	X	X	X	X	X	
Pregnancy Test ³	X	X ⁴		X ⁴	X ⁴	X ⁴	X ⁴	X ⁴	X ⁴	X ⁴	X ⁴	X	
Hematology ³	X	X ⁴		X ⁴	X ⁴	X ⁴	X ⁴	X ⁴	X ⁴	X ⁴	X ⁴	X	
Chemistry ³	X	X ⁴		X ⁴	X ⁴	X ⁴	X ⁴	X ⁴	X ⁴	X ⁴	X ⁴	X	
Coagulation Parameters ³	X	X ⁴		X ⁴	X ⁴	X ⁴	X ⁴	X ⁴	X ⁴	X ⁴	X ⁴	X	
Thyroid Function ³	X	X ⁴		X ⁴	X ⁴	X ⁴	X ⁴	X ⁴	X ⁴	X ⁴	X ⁴	X	
Urinalysis ³	X	X ⁴		X ⁴	X ⁴	X ⁴	X ⁴	X ⁴	X ⁴	X ⁴	X ⁴	X	
Cytokines ⁵		X	X	X	X	X	X	X	X	X	X		
JTX-2011 ⁶		X		X	X	X	X	X	X	X	X		
Nivolumab ⁷ (Part D only)		X		X	X	X	X	X	X	X	X		
Pembrolizumab ⁸ (Part H only)		X		X	X	X	X	X	X	X	X		
Post-Progression Nivolumab or Pembrolizumab (Part C only)													
IP ⁵	X	X	X	X	X	X	X	X	X	X	X		
TE ⁵	X	X	X	X	X	X	X	X	X	X	X	X	
PK ⁵		X	X	X	X	X	X	X	X	X	X	X	
ADA ⁵		X	X	X	X	X	X	X	X	X	X	X	
NAb ⁵		X	X	X	X	X	X	X	X	X	X	X	
DNA Blood Sample ⁵		X	X	X	X	X	X	X	X	X	X	X	
RNA Blood Sample ⁵		X	X	X	X	X	X	X	X	X	X	X	
Archival Tumor ⁵	X												
Fresh Tumor Biopsy ⁵	X			X ⁹									
Radiologic Assessment ¹⁰	X											X ¹¹	X ¹²
ConMeds	X	X	X	X	X	X	X	X	X	X	X	X	
AEs	X	X	X	X	X	X	X	X	X	X	X	X	
Optional Brain MRI ¹⁴	X												
Survival Status													X ¹⁵

See Table 17

Jounce Therapeutics, Inc.

Parts C, D, and H Footnotes (q3w):

- ¹ A complete physical exam is required at Screening and End of Treatment; otherwise a targeted physical exam is acceptable per institutional guidelines. Height to be calculated at screening visit only.
- ² Vital signs to include temperature, heart rate, respiratory rate, blood pressure, and oxygen saturation. Vital signs should be taken prior to and at the end of JTX-2011 infusion.
- ³ Refer to Section 8.8 for specific lab parameters. Pregnancy test can be serum or urine.

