- ⁴ Do not need to be repeated if collected within 72 hours prior to visit.
- ⁵ Refer to the Study Lab Manual for processing shipping instructions. For specific blood sampling time points, refer to Table 18 (Part C), Table 20 (Part D), or Table 20 (Part H).
- ⁶ Subjects should be observed for at least 1 hour post-infusion.
- ⁷ Subjects should be observed for at least 1 hour post-nivolumab infusion.
- ⁸ Subjects should be observed for at least 1 hour post-pembrolizumab infusion.
- ⁹ Part C only. On-treatment biopsies can be collected any time after dosing on C2D1 and prior to dosing on C3D1.
- ¹⁰ Response will be determined by RECIST (Version 1.1) or modified RECIST (for mesothelioma subjects in Part C only) every 9 weeks (-10 days) prior to Day 1 of every 3rd cycle (e.g. C4, C7, C10, etc.). The imaging interval may be increased to every 12 weeks with a +/- 3 week window for subjects who remain on study treatment for \geq 24 months. The same method of assessment used at baseline should be used throughout the study.
- ¹¹ Only required for subjects whose last assessment was $>$ 9 weeks.
- ¹² For subjects discontinuing treatment for reasons other than disease progression, radiologic assessment will be conducted every 12 weeks (\pm 2 weeks) during the long-term follow-up period until confirmed disease progression or another anti-cancer therapy is initiated.
- ¹³ Adverse events will be followed up to 28 days post last dose. As the EOT visit can occur anywhere between 14-28 days post last dose, any outstanding AEs at the time of the EOT visit can be followed via other contact (e.g., phone or email) up to 28 days post dose. If an SAE occurs more than 28 days after last dose administered, the event will only be followed if assessed to be at least possibly related to study drug.
- ¹⁴ Optional Brain MRI to determine eligibility of subjects with documented history of brain metastasis.
- ¹⁵ Survival can be followed via phone call or email, a clinic visit is not required.
- ¹⁶ JTXP previously collected for protocol version 5.0.

Table 16: Phase 2 q6w in Parts C (JTX-2011), F (JTX-2011 + Ipilimumab), and H (JTX-2011 + Pembrolizumab)

	Screening	Cycle 1		Cycle 2		Cycle 3		Cycle 4		Cycle 5 and Beyond		End of Treatment 28 ± 7 days post last dose	Long-Term Follow-up Every 12 weeks post-last dose (± 2 weeks)
		Day 1	Day 2	Day 1	Day 22 ± 3	Day 1 ± 3	Day 22 ± 3	Day 1 ± 3	Day 22 ± 3	Day 1 ± 3	Day 22 ± 3		

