- ⁵ Refer to the Study Lab Manual for processing/shipping instructions. For specific blood sampling time points, refer to Table 18 (Part C), Table 22 (Part F), or Table 22 (Part H).
- ⁶ Subjects should be observed for at least 1 hour post-JTX-2011 infusion.
- ⁷ Subjects should be observed for at least 1 hour post-ipilimumab infusion.
- ⁸ Subjects should be observed for at least 1 hour post-pembrolizumab infusion.
- ⁹ Parts C and F only. On-treatment biopsies can be collected any time after dosing on C2D1 and prior to the C2D22 visit.
- ¹⁰ Response will be determined by RECIST (Version 1.1). Prostate cancer lesions to be assessed per the PCWG2 guidelines (Scher 2008). The same method of assessment used at baseline should be used throughout the study.
- ¹¹ Response will be determined by RECIST (Version 1.1) every 9 weeks (-10 days), or approximately every 1.5 cycles (e.g., mid-Cycle 2, end of Cycle 3, mid-Cycle 5, end of Cycle 6, etc.). The imaging interval may be increased to every 12 weeks with a +/- 3 week window for subjects who remain on study treatment for ≥ 24 months.
- ¹² cancer subjects to have radiographic imaging every 12 weeks (-10 days) or approximately at the end of every 2 cycles.
- ¹³ Only required for subjects whose last assessment was > 9 weeks (or > 12 weeks for prostate cancer subjects).
- ¹⁴ For subjects discontinuing treatment for reasons other than disease progression, radiologic assessment will be conducted every 12 weeks (± 2 weeks) during the long-term follow-up period until confirmed disease progression or another anti-cancer therapy is initiated.
- ¹⁵ Adverse events will be followed up to 28 days post last dose. As the EOT visit can occur anywhere between 14-28 days post last dose, any outstanding AEs at the time of the EOT visit can be followed via other contact (e.g., phone or email) up to 28 days post dose. If an SAE occurs after last dose administered, the event will only be followed if assessed to be at least possibly related to study drug.
- ¹⁶ Optional Brain MRI to determine eligibility of subjects with documented history of brain metastasis.
- ¹⁷ Survival can be followed via phone call or email, a clinic visit is not required.
- ¹⁸ For subjects with prostate cancer only.
- ¹⁹ Weight required for Parts F and H subjects only.
- ²⁰ Weight required for Part H subjects only.

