## **8. ENDPOINT DEFINITIONS AND DERIVATIONS**

### **8.1 SAFETY DEFINITIONS AND ENDPOINTS**

#### **8.1.1 ADVERSE EVENT ENDPOINTS**

Adverse events will be categorized by pre-existing, treatment emergent and post treatment.

- Pre-existing AEs are designated to events that occur prior to the first dose of study drug(s) or observed prior to first dose but did not increase in NCI CTCAE toxicity grade during treatment period.
- Post-treatment adverse events will be any adverse events reported outside the 28 day post dose treatment window until the end of study participation. Any subsequent non-protocol treatment for the cancer diagnosis will end the potential study drug(s) adverse event data collection.
- Treatment-Emergent Adverse Events (TEAEs) are designated to events that occur after the start of study drug(s) and on or before 28 days after final dose of study drug, and were not observed prior to start of treatment; Or if the event was observed prior to the start of study drug but increased in NCI CTCAE grade after either the start of study drug or prior to 28 days after the final dose of study drug. Pre-existing adverse events may be reclassified as TEAEs if the frequency of the event increases during treatment.
- Treatment Related TEAEs will include those TEAEs which are possibly or probably related to study drug(s) as designated by the investigator. Events having a missing relatedness will be designated as definitely related on tables but the listing will display the data as collected. Relationship may be attributed by JTX-2011 and/or nivolumab/ipilimumab/pembrolizumab and will be displayed separately.
- Serious adverse events (SAEs) will include all events classified as serious on the eCRF. The electronic database used to enter data at the site (i.e., RAVE / iMedidata) will be deemed as the complete report for adverse event information. The pharmacovigilance database will be reconciled against the EDC.

- Infusion related reactions (IRRs) may be captured as an adverse event as well as the symptoms that cause the IRR. Symptoms of IRRs are events occurring shortly after or during the study drug infusion. Symptoms may include but are not limited to: flushing, headache, nausea, fever, chills, dyspnea, rash, hypotension, wheezing, coughing, tachycardia. Any sign/symptom determined to be associated with an IRR may be counted as such in adverse event reporting. The highest grade sign/symptom must be associated with the IRR preferred term.

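### New non-serious AEs starting between an early End of Treatment visit and day 28 have no clear recording rule, although the SAP counts treatment-emergent AEs to day 28

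*Protocol*

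**What the plan says.** **End of AE recording.** Protocol 8.14.2: "All AEs will be recorded from the time of signed informed consent until the End of Treatment visit". The same sentence times that visit at 28 ± 7 days after the last dose of any study agent.

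**Timing of the EOT visit.** The synopsis, Section 7, Section 7.4 and 8.14.2 all give 28 ± 7 days. So do the column heads of Table 15 ("28 ± 7 days post-last dose") and Table 16 ("28 ± 7 days post last dose"). The AE footnotes of those two tables differ from their own heads: "As the EOT visit can occur anywhere between 14-28 days post last dose, any outstanding AEs at the time of the EOT visit". The matching footnotes elsewhere agree with the heads. Table 13 (Part E) has "As the EOT visit can occur anywhere between 21-35 days post last dose any ongoing AEs at the time of the EOT visit", and Table 14 (Part G) has "As the EOT visit can occur anywhere between 21-35 days post last dose, any outstanding AEs at the time of the EOT visit". Table 17 (Part C after progression) also uses 21 to 35 days.

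**After an early visit.** Each of these footnotes opens by setting AE follow-up at 28 days after the last dose. Each then says that AEs already outstanding (Tables 14 to 17) or ongoing (Table 13) at the visit *can* be followed by phone or email to day 28.

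**Serious AEs.** Protocol 8.16.4 records all SAEs, related or not, for 28 days after the final dose if no new therapy starts. The Table 16 footnote reads differently: "If an SAE occurs after last dose administered, the event will only be followed if assessed to be at least possibly related" to study drug.

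**Analysis window.** SAP 8.1.1 defines treatment-emergent AEs (TEAEs) as events after the start of study drug and "on or before 28 days after final dose of study drug". SAP 3.2.1 takes safety data to the same 28 days, using whatever is available.

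**The concern.** Collection and analysis end at different points. The analysis window runs to day 28. Under 8.14.2, collection of non-serious AEs runs to a visit that may fall a week earlier, or two weeks earlier if a site works from the Table 15 or 16 footnote. The only text bridging the gap concerns events already known at the visit. Following a known event to its outcome is a different task from asking about new ones.

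Safety and tolerability are primary objectives of every part. A subject with an early visit and no later contact would be counted as having no further TEAE when nobody asked. An error of that kind can only lower the TEAE, related-TEAE and immune-related AE frequencies. It matters most for subjects who stop after one or two doses, because the post-dose window is then most of their treatment-emergent time.

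**Working it through.** The plan gives no figure to reproduce. The check is a comparison of texts followed by day arithmetic.

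**1. EOT window.** 28 − 7 = 21 and 28 + 7 = 35, so the general rule is day 21 to 35. The Table 15 and 16 footnotes say day 14 to 28. The two ranges share only days 21 to 28.

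**2. Is there a recording rule for a new non-serious AE after an early EOT visit?**

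| Text | Covers it? |
|---|---|
| 8.14.2, main rule | No: recording ends at the visit |
| 8.14.2, telephone provision | No: it replaces an EOT visit the subject cannot attend |
| Footnotes, opening sentence | Arguably: 28 days, but worded as follow-up |
| Footnotes, phone or email sentence | No: optional, and only for AEs present at the visit |
| Tables 11 and 12, post-treatment row | No: ongoing AEs only |
| 7.5, long-term follow-up | No: survival, treatment-related SAEs and, for some subjects, scans |
| 8.16.4 | No: SAEs only |

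One sentence points towards coverage to day 28. None clearly requires it.

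**3. Size of the gap.** With the EOT visit on day E, and recording stopped there:

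uncovered days = max(0, 28 − E)

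| E | Uncovered days | Share of the 28 days |
|---|---|---|
| 14 (outlying footnote) | 14 | 50% |
| 21 | 7 | 25% |
| 28 or later | 0 | 0% |

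A visit on days 29 to 35 has the opposite effect: up to 35 − 28 = 7 days of recorded AEs fall outside the TEAE window.

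**4. Share of the whole treatment-emergent period.** For q3w dosing with k doses, the period is 21 × (k − 1) + 28 days.

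| Doses | Period (days) | 7-day gap | 14-day gap |
|---|---|---|---|
| 1 | 28 | 25% | 50% |
| 2 | 49 | 14.3% | 28.6% |
| 3 | 70 | 10% | 20% |
| 6 | 133 | 5.3% | 10.5% |

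**5. Average gap (assumption).** The documents give no EOT dates. If visits were spread evenly over days 21 to 35, half would fall before day 28 with a mean gap of 3.5 days, so the overall mean is 0.5 × 3.5 = 1.75 days (1.75/28, about 6%). Depending on actual visit dates, this could be anywhere from 0 to 7 days.

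These are days without a clear collection rule, not counts of events. The documents give no AE rate from which to convert them.

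**The case against.** The strongest reply is that coverage to day 28 is evidently intended. The footnotes open with a 28-day follow-up statement that is not limited to ongoing events, and they supply the means of contact. This stands in part. A reader might infer that events after an early visit are lost, and the documents do not support that: sites may well have recorded them. What remains is that 8.14.2 says otherwise and that the operative sentence is optional and limited to existing AEs.

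Second, day 14 is an outlier. The synopsis, Section 7, 7.4, 8.14.2, both column heads and Table 17 all agree on 28 ± 7 or 21 to 35. This stands. The 14-day figures apply only to a site that followed the footnote against its own column head.

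Third, a reader might infer that Phase 2 tolerability rests on a shorter observation window than Phase 1. That is not shown. 8.14.2 and the column heads apply 28 ± 7 to Phase 2 as well, Table 17 is itself a Part C table, and the 21-to-35 footnotes in Phase 1 come from Parts E and G only.

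Fourth, a reader might infer that the SAP asserts complete observation of all 28 days. It does not. SAP 8.1.1 classifies events by date and lets later non-protocol cancer treatment end AE collection, and 3.2.1 relies on available data. The fair criticism is narrower: the SAP does not disclose how many subjects stopped being asked before day 28.

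Finally, the Table 16 SAE sentence might suggest that unrelated SAEs go unrecorded after the last dose. 8.16.4 contradicts that. In the copy reviewed the Table 16 footnote list is disordered, so the missing day count should be checked against the original. Table 16 also has little analytic weight: SAP Section 4 says Parts F and H never opened, and the SAP's Part C cohorts, C01 to C05, are all q3w.

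**Conclusion.** The point holds as a gap in the collection rule and an inconsistency in the EOT window, not as demonstrated bias. Non-serious AEs that start between an early EOT visit and day 28 may be under-ascertained for up to 7 days under 28 ± 7. That is 25% of the post-dose window, and 10% of treatment-emergent time after three q3w doses. The 14-day figure applies only if the outlying footnote was followed.

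This rests on reading 8.14.2 as written and on sites making no further contact after the visit. Any effect lowers TEAE incidence. Its occurrence and size, and the number of subjects affected, cannot be computed because the documents give neither EOT dates nor AE rates. SAEs are protected by 8.16.4. In Phase 2 the analysis impact is mainly Parts C and D under Table 15. The point deserves correction because safety is a primary objective and the remedy is cheap.

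**What to change.** - **Protocol, EOT window.** Reconcile 7.4, 8.14.2, the column heads and the AE footnotes of Tables 15 and 16 so that one window is stated throughout.
- **Protocol, AE recording.** State in 8.14.2 and the footnotes that new as well as ongoing AEs are recorded through day 28 after the last dose, or to the start of new anticancer therapy if that is earlier. Where the EOT visit falls before day 28, use the phone or email contact the footnotes already allow.
- **Protocol, SAEs.** Reconcile the Table 16 SAE sentence with 8.16.4.
- **SAP.** Report, by part and cohort, the number of subjects whose last AE contact was before day 28. This needs no new procedure and remains possible if visits are already complete.

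The cost is a wording change, one brief contact per subject with an early EOT visit, and one extra line in the safety tables. TEAE rates may come out slightly higher.
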